#### **Screening period**

During the screening period (0-4 weeks), all participants are assessed to determine whether they meet the eligibility criteria. Retrospective data are collected for reference regarding the clinical symptoms/findings and laboratory parameters before the first dose of Nucala (at least 96 weeks [approximately 2 years] before). These retrospective data should be from physician source/medication record. By using the retrospective data,

information could be provided about the change from pre-Nucala exposure to the end of this study, of which a period would be approximately 4 years.

Any participant who completes assessments during the screening period but does not continue in the study beyond Baseline or is subsequently found to be ineligible for the study prior to Baseline, is classified as Screen Failure. Information collected for the participant classified as Screen Failure is detailed in the guideline for eCRF entry. Rescreening is permitted once only.

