#### 3.4. Variables

The investigator will collect information about the following variables wherever possible and record it on the eCRF. The timing of collecting information is listed in Section 9.1 (Appendix 1) (SoA).

- Demography: Age, sex, body weight, height, EGPA severity classification\*, and medical history/comorbidity
- \*Defined by Japan Intractable Diseases Information Center (Japan Intractable Diseases Research Foundation)
- Administration status of Nucala for EGPA, including product formulation information
- Concomitant medications and therapies
- Adverse events, SAEs, and AESI \*
- \*AESI: hypersensitivity (including anaphylaxis), infections and malignant tumors, defined as safety specifications in the Japanese RMP
- Clinical symptoms (only disease activities relevant to EGPA in systemic vasculitis assessed) of the following 9 organ systems [Sada, 2014]:
  - 1) Systemic
  - 2) Skin
  - 3) Mucous membranes/eyes
  - 4) Ear, nose and throat (ENT)
  - 5) Chest
  - 6) Cardiovascular

- 7) Abdominal
- 8) Renal
- 9) Nervous
- Hospitalization for EGPA-related events
- Emergency room/unscheduled visit for EGPA-related events
- Asthma exacerbation as defined below:
  - 1) Exacerbation of bronchial asthma which requires hospitalization
  - 2) Exacerbation of bronchial asthma which requires emergency room visit
  - 3) Exacerbation of bronchial asthma which requires the use of systemic steroids\*

When a participant requires continuous administration of steroids systemically, in concrete terms, orally, intravenously or intramuscularly, for  $\geq 3$  days. However, as for intramuscular injection, it must also include a continuous administration of dexamethasone sodium phosphate or betamethasone sodium phosphate for  $\geq 3$  days, or one or more doses of triamcinolone acetonide.

When a participant receiving the maintenance therapy with systemic steroids requires doubling the maintenance dose for  $\geq 3$  days for exacerbation of bronchial asthma.

Exacerbations that occurred <7 days from the last exacerbation were treated as a continuation of the same exacerbation.

- Clinical laboratory parameters:
- Lung function: (with reason for examination of pulmonary function)

Pre- and post-bronchodilator values will be collected as respective separate categories. If it is not known whether the reading is pre- or post-bronchodilator, this will be collected as unknown.

- CCI

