#### 9. APPENDIX

# 9.1. APPENDIX 1: SCHEDULE OF ACTIVITIES (SOA)

Procedure	Screening		Observation period			Follow-up 
Time period for which data should be collected at	Up to 4 we	eks before Week 0 	Week 0	Week 12 to 96;	Early	Up to 96 weeks
usual EGPA healthcare visits,	(Screening  )	(Retrospective data 	Baseline	no more frequently than	withdrawal	after Week 0
if this is possible		collection)		every 12 weeks (±4weeks)		
Informed consent	X 					
Inclusion and exclusion criteria	Χ					
Demography	X					
Administration status of Nucala for EGPA	X		Χ	Χ	Χ	X 5
Concomitant medication	X	X6	Χ	Χ	Χ	X
Concomitant therapies	X	X 	Χ	X	Χ	X
Adverse events	X		+			→
Clinical symptoms		Χ	Χ	Χ	Χ	X
Hospitalization for EGPA-related events		X8	Χ	X	Χ	X
ER/Unscheduled visit for EGPA-related events		X8	Χ	Χ	Х	X
Asthma exacerbation		X8	Χ	Χ	Х	X
Clinical laboratory parameters  , if performed		Х	Χ	Χ	Χ	X
Lung function, if performed		Х	Χ	X	Χ	X
Ejection fraction, if performed		Х	Χ	Χ	Χ	X
Pregnancy reporting			•		-	
EGPA recurrence						X

- 1. The follow-up period is only applicable for participant who discontinued the treatment. If drug-related adverse events occurred, contact the sponsor.
- 2. Screening and Week 0 can occur on the same day.
- 3. Retrospective data within 12 weeks (otherwise specified) before the first dose of Nucala for EGPA.
- 4. Informed consent must be obtained prior to start of any study's procedure.
- 5. Only for in case of receiving the re-treatment of Nucala.
- 6. Only for other biological products, Nucala for asthma, corticosteroid, immunosuppressants, and immunoglobulin.
- 7. Only for EGPA therapies.
- 8. Number of events within 48 weeks before the first dose of Nucala for EGPA.
- 9. Haematological parameters tested are:

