4.3.1.2.5. Average daily dose of OCS and Dosing categories

Endpoints

- Average daily dose (prednisolone-equivalent) of OCS
- The proportion of participants in the dosing categories relative to average daily OCS (prednisolone-equivalent)

Specification

To calculate the dose of OCS by prednisolone equivalent, multiply by the following coefficients.

Generic name	GSK Drug Code	Prednisolone equivalent value	Coefficient
Hydrocortisone	00028601	20	0.250
Hydrocortisone succinate	00028602	20	0.250
Cortisone acetate	00014602	25	0.200
Prednisolone	00016201	5	1.000
Prednisolone succinate	00016203	5	1.000
Methylprednisolone	00049601	4	1.250
Methylprednisolone succinate	00049602	4	1.250
Triamcinolone	00031901	4	1.250
Triamcinolone acetonide	00031902	4	1.250
Dexamethasone	00016001	0.75	6.667
Dexamethasone phosphate	00016002	0.75	6.667
Paramethasone acetate	00066402	2	2.500
Betamethasone	00008501	0.75	6.667
Betamethasone phosphate	00008502	0.75	6.667

Average daily dose of OCS for each participant will be calculated by 12-weekly periods and the retrospective period as:

Total dosage of OCS (mg) / Total duration of administration of OCS (day) Total duration of administration is defined as:

• By 12-weekly period

Last date of each period - later date of (first date of each period or start date of OCS) +1

12-weekly period is described in Section 6.2.4. If OCS is administered and then OCS is no longer required on the last date of each period, 0 mg will be imputed.

• Retrospective period

Last date of retrospective period–later date of (start date of retrospective period or start date of OCS) + 1

Average daily OCS in the retrospective period will be calculated if a participant uses OCS in the retrospective period, otherwise average daily OCS will be 0 mg. If OCS is administered and then OCS is no longer required on the last date of the retrospective period, 0 mg will be imputed.

Over observation period

Last day of observation period (Week 48 for interim analysis, if participant is on-going on observation period) - later date of (date of dose of Nucala at Week 0 or start date of OCS) +1.

If the date of dose of Nucala at Week 0 is missing, the latest available date between the date of screening visit and the date of visit at week 0 will be used for calculation of observation period. If OCS is administered and then OCS is no longer required during the observation period, 0 mg will be imputed.

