When more than one OCS is administered to a participant in the same period, the sum of OCS doses will be used as daily OCS dose.

Summary statistics of average daily dose of OCS will be calculated by the retrospective period and 12-weekly periods. Average daily dose of OCS percent change from Week 0 and from retrospective period will also be summarized by 12-weekly periods. A box plot and a line plot of the median average daily dose of OCS will be produced.

Average daily dose of OCS percent change from Week 0 and from retrospective period is calculated as:

Percent change = ((average daily dose of OCS at each 12-weely period - average daily dose of OCS at Week 0 (or retrospective period))/ average daily dose of OCS at Week 0 (or retrospective period))*100 (%)

The frequency and percentage of participants in the following dosing categories relative to average daily OCS will be summarized by the retrospective period and 12-weekly periods. The denominator of the frequency is the TP. A line plot of the percentage of patients with 0 mg/day of average daily OCS will be presented.

Daily OCS dosing category:

- 0 mg/day, 0 mg/day < \leq 4.0 mg/day, 4.0 mg/day < \leq 7.5 mg/day, 7.5 mg/day <
- $0 \text{ mg/day} \le 2.0 \text{ mg/day}, 2.0 \text{ mg/day} \le 4.0 \text{ mg/day}$

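### The SAP's 0 mg default for pre-Nucala OCS has no branch for unknown status, so an unavailable medication record would be counted as steroid-free

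*SAP*

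**What the plan says.** SAP 4.3.1.2.5 gives the retrospective rule in two branches. A dose is worked out for participants with OCS use in that window; "otherwise average daily OCS will be 0 mg". For the dosing categories, summarised for the retrospective period and the 12-weekly periods, it adds: "The denominator of the frequency is the TP". The same section plans summary statistics of the average dose, percent change from Week 0 and from the retrospective period, and a line plot of the percentage of participants at 0 mg/day. SAP 4.3.1.3 plans no sensitivity analysis for the secondary endpoints.

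On collection, Protocol 3.1 (Screening period) says: "These retrospective data should be from physician source/medication record". Footnote 3 of the Schedule of Activities (Protocol 9.1) sets the window: "Retrospective data within 12 weeks (otherwise specified) before the first dose of Nucala for EGPA". Footnote 6 lists the retrospective medications, and corticosteroid is among them: "Only for other biological products, Nucala for asthma, corticosteroid, immunosuppressants, and immunoglobulin". Protocol 3.4 introduces all study variables, concomitant medications included, with: "The investigator will collect information about the following variables wherever possible and record it on the eCRF".

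**The concern.** The rule separates OCS use from everything else. Everything else holds two different situations: the record was checked and shows no OCS, or the record could not be obtained. For the first, 0 mg/day is the correct value. For the second, the value is unknown. With the whole Treated Population as denominator there is no category for unknown, so a program that follows the rule would place such a participant at 0 mg/day.

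Gaps are foreseeable. The 12-week window closes at the first dose of Nucala, at least 96 weeks before entry, and the data come from existing records.

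The retrospective value is the only pre-Nucala reference for OCS, and Protocol 3.1 says the retrospective data are there to describe change from before Nucala to the end of the study. A false zero understates the starting dose and overstates the starting steroid-free share, so the later reduction looks smaller than it was.

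**Working it through.** **What the plan supplies.** It gives no figure for missing retrospective records or for the pre-Nucala steroid-free share. The only usable number is the planned size of about 120 (Protocol 3.5, SAP 5). That figure reproduces: the smallest n with 1 − 0.985^n ≥ 0.80 is 107 (probability 0.8015), and 107/0.90 = 118.9, so 119, or about 120.

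**Assumptions, not document figures.**
- m = share with an unavailable retrospective OCS record: 5%, 10%, 20%.
- p0 = true pre-Nucala steroid-free share: 10%.
- Missingness unrelated to dose (relaxed in step 4).

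**Step 1. Share shown at 0 mg/day** = p0 + (1 − p0) × m.
- m = 5%: 0.10 + 0.90 × 0.05 = 14.5%
- m = 10%: 0.10 + 0.90 × 0.10 = 19%
- m = 20%: 0.10 + 0.90 × 0.20 = 28%

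**Step 2. Retrospective mean shown** = (1 − m) × true mean. If the true fall in the mean were 60% (assumption), the fall computed from the period means would be 1 − 0.40/(1 − m).

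**Step 3. Individual percent change.** The SAP formula divides by the retrospective dose. At 0 it is undefined, so a false zero removes the participant from this summary. The number with a defined value is 120 × (1 − p0) × (1 − m).

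| m | At 0 mg/day, of 120 | Share | Mean shown / true mean | True 60% fall in mean appears as | Percent change defined, of 120 |
|---|---|---|---|---|---|
| 0% | 12 | 10% | 1.00 | 60% | 108 |
| 5% | 17.4 | 14.5% | 0.95 | 57.9% | 102.6 |
| 10% | 22.8 | 19% | 0.90 | 55.6% | 97.2 |
| 20% | 33.6 | 28% | 0.80 | 50% | 86.4 |

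The median moves the same way. If users' doses are lognormal with median 10 mg/day and log-SD 0.6 (assumption), the retrospective median falls from about 9.2 to about 8.8, 8.4 and 7.4 mg/day at m = 5%, 10% and 20%. Under the same assumptions the median individual percent change stays at −60%; only its n shrinks.

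**Step 4. Without the independence assumption.** The share shown at 0 mg/day is p0 + m × (share of true users among those missing). With p0 = 10% it lies between the larger of p0 and m, and p0 + m:
- m = 5%: 10% to 15%
- m = 10%: 10% to 20%
- m = 20%: 20% to 30%

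The mean shown is the true mean minus m times the true mean dose of those missing. The error therefore depends on who is missing as well as how many, but it cannot raise the retrospective mean or lower the 0 mg/day share.

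**The case against.** The strongest case on the other side has five parts.

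1. **The condition in the SAP is use, not recorded use.** A reader might infer that the SAP expressly zeroes anyone without a recorded OCS entry. It does not say so; it is silent on unavailable records. This stands as a limit on wording. But a derivation sees only recorded data, and the second branch covers every case outside the first.

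2. **Records may be nearly complete.** Retrospective corticosteroid collection is expressly scheduled, and that row carries no if-performed qualifier, unlike laboratory tests, lung function and ejection fraction. Every participant had completed the PMS study (Protocol 3.3.1). Protocol 9.2.5 allows earlier medical records to be requested. The Schedule of Activities phrase "if this is possible" concerns collection at usual visits and is not evidence of absent records. All this stands. It makes a small missing share plausible but does not establish zero, and the documents do not say that PMS data are reused.

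3. **Percent change is not falsified.** A reader might infer that every before/after OCS result is biased. Individual percent change is not given a false value, because it is undefined at zero. This stands. Those participants do, however, drop out unidentified among true non-users.

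4. **The stakes are limited.** The study is descriptive. The secondary OCS endpoints concern the observation period, retrospective data are collected for reference, Week 0 is a second comparator, and Protocol 5 already cautions on effectiveness. This stands and limits the weight of the point.

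5. **A rule may exist elsewhere.** The available SAP text passes from 6.2.4 to 6.2.6, and the eCRF is not available. A rule in 6.2.5, or an eCRF item separating none from not available, cannot be excluded. The partial-date rules in 6.2.6 impute dates, not OCS status.

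**Conclusion.** The point holds as a gap in a stated derivation rule. As written, and in the text available, SAP 4.3.1.2.5 would turn an unknown retrospective OCS status into 0 mg/day. The retrospective mean, median, dose categories and 0 mg/day percentage are exposed. Observation-period OCS results, change from Week 0 and the safety endpoints are not.

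The size is conditional. With p0 = 10% and missingness unrelated to dose, 5%, 10% or 20% missing moves the 0 mg/day share to 14.5%, 19% or 28% and lowers the retrospective mean by 5%, 10% or 20%. With no missing records there is no effect.

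Two stronger conclusions are not supported. A reader might infer that the pre/post comparison is in fact distorted; the documents give no missing share, so this is a risk and not a finding. A reader might also infer that the rule favours Nucala; a false zero works the other way and understates later steroid reduction.

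**What to change.** Amend SAP 4.3.1.2.5 as follows:

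- Assign 0 mg/day for the retrospective period only when the source record for that window was reviewed and shows no OCS.
- Set the retrospective average to missing when OCS status is unknown.
- Use participants with known retrospective OCS status as the denominator for the retrospective dose categories and the retrospective 0 mg/day percentage, and report the number missing.
- State that percent change from the retrospective period is not calculated when the retrospective dose is 0, and report how many participants this affects.

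If 6.2.5 already holds such a rule, a cross-reference would cover the part it addresses.

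The cost is a short SAP change and one derivation flag, plus possibly one data query if the eCRF does not separate none from not available. The retrospective n becomes slightly smaller: of 120, it would be 114, 108 or 96 at 5%, 10% or 20% missing. If nothing is missing, the retrospective doses and category percentages do not change.

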4.3.1.3. Sensitivity analyses

Not Applicable

4.4. Exploratory Endpoint(s) Analyses

CCI			

CCI		

CCI			

CONFIDENTIAL

4.5. Other Safety Analyses

4.5.1. Extent of Exposure

The frequency and percentage of exposure to Nucala will be summarized for each of the following categories by the observation period and the follow up period, based on the TP. The extent of exposure will also be listed.

- Nucala 300mg SC only
- Other than the above (e.g., dose reduction of Nucala)

The duration in days between the first dose of Nucala for EGPA in the retrospective period and the last dose of Nucala in the observation period will be summarized.

4.5.2. Adverse Events

Refer to the primary endpoint analyses.

4.5.2.1. COVID-19 Assessment and COVID-19 AEs

AEs of all participants with COVID-19 will be listed for the TP.

4.5.2.2. Impact of COVID-19 Pandemic on Safety Results

Not Applicable

4.6. Other Analyses

4.6.1. Profile plot

A participant profile plot including the following items will be created.

- OCS daily dose
- No clinical symptoms as assessed by 9 organ-systems at all
- EGPA relapse
- An increased dose or addition of immuno-suppressive therapy
- Hospitalization related to EGPA worsening

4.6.2. Immuno-suppressive Therapy

The frequency and percentage of participants with no immuno-suppressive therapy will be summarized by the retrospective period and12-weekly periods. 12-weekly period is described in Section 6.2.4. A line plot of the percentage of patients with no immuno-suppressive therapy will be presented.

4.6.3. EGPA Remission

EGPA remission is defined as each of the combinations of the clinical symptoms as assessed by 9 organ-systems and average daily dose of OCS.

- Participants with no clinical symptoms as assessed by 9 organ-systems
- Participants with no "worsening" clinical symptoms as assessed by 9 organ-systems
- Participants with average daily dose of OCS in $\leq 4.0 \text{ mg/day}$

• Participants with average daily dose of OCS in 0 mg/day

The frequency and percentage of participants in EGPA remission by EGPA remission period will be summarized. Line plots by EGPA remission period will also be produced for the proportion of participants with average daily dose of OCS in ≤ 4.0 mg/day and in 0 mg/day. The plots will be displayed for the participants with no clinical symptoms as assessed by 9 organ-systems and no "worsening" clinical symptoms separately.

The period for EGPA remission is defined as follows:

EGPA remission period	Clinical symptoms as assessed by 9 organ- systems	Average daily dose of OCS
Week 12/Weeks 9-12	Week 12	Weeks 9-12
Week 24/Weeks 21-24	Week 24	Weeks 21-24
Week 36/Weeks 33-36	Week 36	Weeks 33-36
Week 48/Weeks 45-48	Week 48	Weeks 45-48
Week 60/Weeks 57-60	Week 60	Weeks 57-60
Week 72/Weeks 69-72	Week 72	Weeks 69-72
Week 84/Weeks 81-84	Week 84	Weeks 81-84
Week 96/Weeks 93-96	Week 96	Weeks 93-96

4.6.4. Subgroup analyses

The following subgroups are of interest in this study. A separate exploratory analysis of the prespecified endpoints within each subgroup will be carried out. Subgroup categories may be further collapsed if there are a small number of participants within a subgroup.

The following subgroups are of interest:

- Period from EGPA diagnosis to Nucala administration (year) (≤ 1, 1 < ≤ 2, 2 < ≤ 5, 5 < ≤ 10, 10 <)
- Severity of EGPA disease (1-2, 3, 4-5)
- Average daily dose (prednisolone-equivalent) of oral corticosteroid (OCS) over the observation period (0 mg/day, 0 < ≤ 4 mg/day, 4 < ≤ 7.5 mg/day, 7.5 mg/day <)
- ANCA (Positive, Negative)
- Immuno-suppressive therapy (Yes, No)

• EGPA disease relapse (Yes, No)

The following will be presented for each subgroup, based on the TP:

- summary of all AEs by the observation period and by the total period (the observation period and the follow-up period)
- frequency of participants with clinical symptom assessed by 9 organ-systems at each assessment visit by the observation period
- frequency of participants with EGPA relapse by the observation period
- summary of average daily dose of OCS at each assessment visit by the observation period
- plot of participants with clinical symptom assessed by 9 organ-systems at each assessment visit by the observation period
- box plot of median of average daily dose of OCS at each assessment visit by the observation period

• line plot of median of average daily dose of OCS at each assessment visit by the observation period In addition, the demographic and baseline characteristics will be summarized for the following subgroups.

- Completion/Discontinuation of the study
- With/Without clinical symptoms as assessed by 9 organ-systems at Week 48 and Week 96

Subgroup	EP1	EP2	EP3	EP4
Period from EGPA diagnosis to Nucala administration	Y	Y	Y	Y
Severity of EGPA disease	Y	Y	Y	Y
Average daily dose (prednisolone-equivalent) of oral corticosteroid (OCS) over the observation period	Y	Y	-	Y
ANCA	Y	Y	Y	Y
Immuno-suppressive therapy	Y	Y	Y	Y
EGPA disease relapse	Y	-	Y	Y

EP1: Proportion of participants with each of the clinical symptoms as assessed by 9 organ-systems EP2: Proportion of participants with EGPA relapse

EP3: Average daily dose (prednisolone-equivalent) of oral corticosteroid (OCS) over the observation period

EP4: Frequency of Adverse events (AEs)

The above categories may be reconsidered a more appropriate level, and additional subgroup categories will be planned in the further analysis.

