- EGPA recurrence is judged by investigator based on the following definitions (only in participants who have been withdrawn from/terminated the Nucala treatment and entered the follow-up period due to symptom improvement per clinical judgement):
  - 1) Initiation/increased dose of OCS

\*The standard definitions for the use of systemic steroids are as follows:

- 2) Initiation/increased dose of immuno-suppressive agents
- 3) Hospitalization in association with the EGPA treatment

Note that EGPA relapse is defined in Section 4.6.

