# 4.7. Subgroup Analysis

The following subgroups are of interest in this study. A separate exploratory analysis of the prespecified endpoints within each subgroup will be carried out. Subgroup categories may be further collapsed if there are a small number of participants within a subgroup.

The following subgroups are of interest:

- Sex
- Age
- Duration of EGPA disease
- Severity of EGPA disease
- Adherence to recommended treatment regimen for Nucala
- Current medical conditions (e.g., presence/absence of asthma, allergic rhinitis, etc.)
- Medical history (e.g., presence/absence of asthma, allergic rhinitis, etc.)
- Prior use of Nucala for asthma

- Previous therapeutic regimen for EGPA disease (e.g., presence/absence of plasma exchange therapy, operation, etc.)
- Prior use of other biological medications
- ANCA
- Favourable treatment response with Nucala
- Immuno-suppressive therapy
- EGPA disease relapse
- Clinical symptoms
- COVID-19 infection

Further details of the subgroup analyses will be provided in the RAP.

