4.3.1.2.2. EGPA Relapse

Endpoint

Proportion of participants with EGPA relapse

Specification

The frequency and percentage of participants with EGPA relapse for the observation period and for the follow-up period will be summarized. The frequency and percentage of participants with EGPA relapse will be categorized as 1 time, 2 times, and \geq 3times, and summarized. The frequency and percentage of EGPA relapse and the events that cause EGPA relapse (1-3 in the Step1 below) will also be summarized. A separate summary will be displayed for the events that cause EGPA relapse. A listing of EGPA relapse will also be produced.

Determination of EGPA relapse

EGPA relapse is defined as any of the following events with worsening EGPA*

- 1) Increased dose of OCS
- 2) Initiation/increased dose of immuno-suppressive agents**
- 3) EGPA treatment with hospitalization

* Worsening of EGPA: new onset of EGPA symptoms or worsening of existing clinical symptoms as assessed by 9 organ-systems.

** Immuno-suppressive agents: If the dose of immuno-suppressive agents increases for the same formulation or if the number of immuno-suppressive agents increases for EGPA treatment.

Event date is defined as:

- 1) Increased dose of OCS: **Date of increased dose**
- 2) Initiation/increased dose of immuno-suppressive agents: Date of initiation/Date of increased dose
- 3) EGPA treatment with hospitalization: Date of hospitalization

The first relapse occurred between two consecutive assessment time points will be counted as EGPA relapse for the first of the two assessment points. When assessment time points are scattered (i.e. Week 24 data is missing due to no clinic visit), events occurred within the last visit date + 84 days will be used as the determination for EGPA relapse.

Definition of Relapse Date

Set the starting point date for each of the following relapse conditions 1) to 3) and calculate the time to relapse (day).

The formula for calculating the time to relapse is relapse date – starting point date + 1

However, if the conditions 1) to 3) overlap, the shortest time (day) until relapse will be used.

1) Increase in OCS dose

- The date of relapse is the date of dose increase.
- The starting point date is the date of the end of dosing immediately before the dose increase or the earliest assessment date without symptoms of EGPA and dose reduction.

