Week 24	2020/7/2	Active or worsening			None
			2020/7/3	Start date of	10 (New
			(Relapse date)	dosing	initiation)

3) Treatment involving hospitalization

- The date of relapse is the date of hospitalization.
- The starting point date is the date of discharge immediately prior to relapse or the earliest assessment date without symptoms of EGPA.

ex1) If there is a discharge date immediately before the relapse, the starting point date is the discharge date immediately before the relapse.

Assessment time points	Assessment date	EGPA symptoms	Date of hospitalization or discharge	Condition of hospitalization or discharge
Nucala start date	2020/1/1	Active or worsening		Ongoing hospitalization
			2020/1/2 (Starting point date)	Date of discharge
Week 12	2020/4/15	None		
			2020/6/13 (Relapse date)	Date of hospitalization
Week 24	2020/7/2	Active or worsening		Ongoing hospitalization

ex2) If there is no discharge date immediately prior to relapse or if there is no discharge date exists (e.g. ongoing hospitalization, incomplete date), the starting point date is the earliest assessment date without symptoms of EGPA.

Assessment time points	Assessment date	EGPA symptoms	Date of hospitalization or discharge	Condition of hospitalization or discharge
Nucala start date	2020/1/1	Active or worsening		
Week 12	2020/4/15 (Starting point date)	None		
			2020/6/13 (Relapse date)	Date of hospitalization
Week 24	2020/7/2	Active or worsening		Ongoing hospitalization

Increased dose of OCS & Initiation/increased dose of immuno-suppressive agents

nmuno-suppr	ressive age	ents will be made as follows.			
	Conditi	on			
Increased dose	The day OCS: In equivale Immuno suppress number	The day after the visit date of Week 0 in this study: OCS: In case of the dose of OCS increased as prednisolone- equivalent Immuno-suppressive agents: In case of the dose of immune- suppressive agents increased for the same formulation or if the number of immune-suppressive agent increased			
Initiation	In case of number this does of admir	In case of an immune-suppressive agent is newly started (or the number of agents is added) after the start date of Nucala. However, this does not apply if the same agent is re-administered after the start of administration of the agent.			
Ν	ucala start d	ate at Week 0	Determination		
		100 mg	Initiation		
50 mg		100 mg	Initiation		
•	50 mg	100 mg	Increase		
•	50 mg	100 mg	Increase		
		50 mg 100 mg	• Initiation & Increase		
•	50 mg	100 mg	Increase		

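### The relapse-by-OCS-dose table classes participants by OCS dose over the same period as the outcome, so relapse at 0 mg/day is low partly by construction

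*SAP*

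**What the plan says.** The subgroup list in SAP 4.6.4 includes "Average daily dose (prednisolone-equivalent) of oral corticosteroid (OCS) over the observation period", cut into 0, above 0 to 4, above 4 to 7.5, and above 7.5 mg/day. The outputs for each subgroup include "frequency of participants with EGPA relapse by the observation period", and the grid marks EP2 (relapse) Y in the OCS row. The grid dashes only OCS dose by OCS dose and relapse by relapse.

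In SAP 4.3.1.2.2, "EGPA relapse is defined as any of the following events with worsening EGPA". The three events are a rise in OCS dose, starting or increasing an immunosuppressant, and hospitalization for EGPA treatment. OCS increases count from "The day after the visit date of Week 0 in this study".

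SAP 4.3.1.2.5 computes the average as total OCS milligrams divided by days. Over the observation period the denominator starts at the "later date of (date of dose of Nucala at Week 0 or start date of OCS") and runs to the last day of the period. It adds: "If OCS is administered and then OCS is no longer required during the observation period, 0 mg will be imputed".

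The subgroup list in Protocol 4.7 names "EGPA disease relapse" but has no OCS-dose subgroup.

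**The concern.** The subgroup is fixed only after the outcome period is over, and the outcome helps to fix it. A participant who is off OCS at Week 0 and receives OCS for a relapse leaves the 0 mg/day class because of that relapse. Only relapses by immunosuppressant or hospitalization without OCS can remain there.

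The table would therefore show few relapses at 0 mg/day, and an excess in the non-zero classes taken together, even if relapse risk had nothing to do with steroid dose. A reader could take this as stable disease in steroid-free participants. The mirror table, average OCS dose by relapse yes/no, shares the overlap, because OCS given for the relapse enters the average.

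**Working it through.** **Plan's own figures.** The documents give no figure for relapse by OCS class. The only one used here is the planned size of about 120. It reproduces: ln(0.20)/ln(0.985) = 106.5, so 107; 107/0.9 = 118.9.

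**Step 1: can an OCS relapser average 0 mg/day?** I read the zero-imputation sentence as 0 mg for the days off OCS, because the denominator runs to the end of the period and not to the OCS end date. Then any intake gives a positive average. An illustrative 10 mg for 3 days over 673 days gives 30/673 = 0.045 mg/day, which is above 0. So the answer is no.

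**Step 2: expected result with no true association.** All inputs are assumptions:
- r: relapse risk, the same at every Week 0 dose
- q: share of relapses that include OCS
- first OCS starts count as increases

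Of those off OCS at Week 0, a fraction rq moves out of the 0 mg/day class. What remains shows r(1−q)/(1−rq). At r = 20%, q = 80% this is 0.04/0.84 = 4.8%.

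| r | q = 50% | q = 90% |
|---|---|---|
| 10% | 5.3% | 1.1% |
| 20% | 11.1% | 2.4% |
| 30% | 17.6% | 4.1% |
| 40% | 25.0% | 6.25% |

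OCS taken for other reasons with probability a, independently of relapse, multiplies numerator and denominator by (1−a) and cancels.

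**Step 3: counts with N = 120, r = 20%, q = 80%.**

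| Off OCS at Week 0 | 0 mg/day class, SAP rule | Classed by Week 0 dose |
|---|---|---|
| 10% (12) | 0.5 of 10.1 | 2.4 of 12 |
| 40% (48) | 1.9 of 40.3 | 9.6 of 48 |
| 60% (72) | 2.9 of 60.5 | 14.4 of 72 |

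In the 40% case there are 24 relapsers overall. The non-zero classes together then hold 24 − 1.92 = 22.08 relapsers among 120 − 40.32 = 79.68 participants, or 27.7%, against 4.8% at 0 mg/day.

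**Step 4: which non-zero class gains?** A simulation of 2,000,000 participants assumed:
- a uniform relapse day and +10 mg/day at relapse
- 40% off OCS at Week 0
- users at 2.5, 5, 7 and 10 mg with weights 0.35, 0.30, 0.20 and 0.15
- the SAP denominator, with the OCS start taken as the on-study start

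| OCS course | 0 mg/day | >0 to 4 mg/day | >7.5 mg/day |
|---|---|---|---|
| 28 days | 4.7–4.8% | 37% | 23% |
| 84 days | 4.7–4.8% | 34% | 40% |
| 168 days | 4.7–4.8% | 18% | 44% |
| to period end | 4.7–4.8% | 7% | 66% |

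The 0 mg/day result does not depend on course length; the others do, so no single figure is claimed for them. In the mirror table relapsers averaged 0.75 to 5.6 mg/day more. Classed by Week 0 dose, every class showed about 20%.

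**Step 5: the other reading of the zero-imputation rule.** Suppose stopping OCS sets the whole average to 0, and a share s of OCS relapsers stop. Among those off OCS at Week 0 the class shows r(1−q+qs)/(1−rq+rqs). At r = 20%, q = 80% this is 4.8% for s = 0, 0.12/0.92 = 13.0% for s = 0.5, and 20% for s = 1.

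**The case against.** **Low stakes.** This is one cell of an exploratory grid in a descriptive study without hypothesis tests. Protocol 5 already urges caution over the effectiveness results, the row label discloses the concurrent window, and SAP 4.3.1.2.2 and 4.6.1 provide a summary of relapse causes, a listing and profile plots. That holds as to weight. But Protocol 5 speaks of selection and sample size, not of this overlap, and the other outputs do not correct this table.

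**All inputs are assumed.** True. The illustrated 0 mg/day figure runs from 1.1% to 25.0%, and a small class may be uninformative: the exact 95% interval is 0 to 30.8% for 0 of 10, and 0.6 to 16.9% for 2 of 40. The direction does not depend on the inputs: for 0 < r < 1 and any q above 0, the class falls below r.

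**First OCS starts may not count.** The recurrence definition in Protocol 3.4 reads "Initiation/increased dose of OCS", whereas the relapse definition names initiation only for immunosuppressants. The worked examples label a move from none to 10 mg as an increase, but only after earlier dosing. This favours counting starts without settling it. If they do not count, the 0 mg/day row stays low by definition under either classing, and the Week 0 remedy alone does not cure it.

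**Side effects and gaps.** A Week 0 dose answers a different question from a period average. If the 48-week interim report used this subgroup, which is not stated, comparability would suffer. The immunosuppressive-therapy row also has relapse marked Y, with no time window, and may carry a parallel overlap. The rule that uses events up to 84 days after the last visit may place a few OCS increases outside the averaging window, which weakens the effect slightly. These points stand but do not remove the overlap.

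**Conclusion.** The concern holds, as a low-severity point. On the natural reading of SAP 4.3.1.2.5, the 0 mg/day class excludes every relapse that included OCS in the period, so its relapse proportion is depressed whatever the true relation to dose. At an assumed 20% risk with 80% of relapses including OCS it shows 4.8%. The excess is certain only for the non-zero classes combined. The size rests on assumed r and q, on counting first OCS starts as increases, and on zero being imputed for days off OCS only. Primary safety results and all analyses of the whole Treated Population are unaffected.

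**What to change.** 1. Define the OCS subgroup by daily prednisolone-equivalent dose on the date of the Week 0 Nucala dose, keeping the cut-points and using the SAP 6.2.4 fallback if that date is missing. The rule must be written out: SAP 4.3.1.2.5 uses a Week 0 OCS value for percent change, but no Week 0 window is defined. Alternatively, keep the on-study subgroup and set its EP2 cell to a dash.
2. State whether the zero imputation applies to days off OCS or to the whole average.
3. State whether a first OCS start from 0 mg counts as an increase for relapse. If not, footnote the 0 mg/day row.
4. Keep OCS dose (EP3) in the relapse row, since the protocol names that subgroup, and footnote that OCS given for the relapse is in the average.

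The cost is SAP wording plus one class variable or one dashed cell, and one or two footnotes. No new data are needed, because OCS is recorded daily (SAP 6.2.4). No protocol text is contradicted, and the closing sentence of SAP 4.6.4 allows categories to be reconsidered. What is lost is the descriptive split of relapse by on-study steroid use and, if the interim report used this subgroup, direct comparability with it.
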